### *Population*

Two hundred HIV-positive pregnant women  $\geq 18$  years of age, or if aged 14-17 are qualified as emancipated minors, with male partners of unknown status, will be recruited from PMTCT B+ programs in Kampala.

### *Eligibility*

For women

- Age  $\geq 18$  or 14-17 years if an emancipated minor (pregnant or have a child)
- Currently pregnant
- Not currently enrolled in an HIV treatment study
- Male partner not known to be HIV-positive or has not tested in the past 3 months
- Able and willing to provide written informed consent
- Able and willing to provide adequate locator information for study retention purposes
- Screening negative for any indication of intimate partner violence or social harm

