In our ongoing study, Obumu (*R01 MH113434*) we are evaluating the impact of secondary distribution of HIV self-testing on male partner engagement in HIV testing, and uptake in HIV care and prevention services. In this evaluation, women were randomized to the intervention arm by providing their partner an HIVST kit, or the control arm, by providing a standard of care letter provided by the clinic. Though qualitative data and informal focus group discussions with men in Obumu, we have learned that disclosure is a major barrier to secondary distribution of HIV self-testing kits from HIV-positive pregnant women to their male partners. We have conducted in-depth interviews and focus group discussions of male partners of pregnant women as part of Obumu, and many men indicate they will be motivated to test for HIV at the ANC clinic if other services are offered, such as syphilis testing and other health services (e.g., blood pressure and visual acuity screening) provided during a wellness visit. We hypothesize that if HIV testing is offered in conjunction with an emphasis on syphilis testing, blood pressure, an eye exam, and COVID-19 symptom screening, this may offset the barriers to either responding to an invitation letter for HIV testing or use of HIV the self-test provided by their female partner and improve their overall uptake of testing for HIV.

By leveraging the findings from Obumu, we propose to enroll a new cohort of 200 HIV-positive pregnant

women with partners of unknown status in order to evaluate whether an invitation to a wellness screening, including dual rapid syphilis and HIV tests, blood pressure, visual acuity screening, COVID-19 symptom screening will overcome male partners reluctance to be tested only for HIV in PMTCT clinics.

Pregnant women in PMTCT do not always have viral load tests obtained or counseling about their results. In the Obumu study, we have found that approximately 30% of women living with HIV did not have a viral load result at months 6-12 post-partum, and of those who did have a viral load obtained, 20% were not virally suppressed. The proportion of post-partum women in Obumu without a viral load increased to over 40% after the COVID-19 shut down, which adds another barrier to ART adherence counseling among women who are facing other challenges with ART continuation after delivery. This could lead to increased risk of breastmilk transmission for women who are not virally suppressed.

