- Design:** Randomized clinical trial  
Up to 6 months of post-partum follow-up
- Population:** 200 HIV-positive pregnant women who have a partner of unknown status and their male partners
- Study Site:** The Infectious Diseases Institute (IDI) Kasangati and Kitebi Health Center III antenatal care (ANC) clinic in Kampala, Uganda
- Approach:** We will recruit pregnant women  $\geq 18$  years accessing ANC and PMTCT B+ programs in Kampala, who have a male partner of unknown HIV status. Women will be randomized 1:1:1:1 to the intervention for male partners (provision of an invitation letter for a wellness visit with dual rapid syphilis and HIV tests, blood pressure, visual acuity screening and COVID-19 symptom screening or an invitation letter for fast track testing at the clinic (the standard of care), and either the intervention of POC VL and same day ART adherence counseling or the standard of care every six months lab-based HIV VL testing. with adherence counseling at their next visit.
- In accordance with MOH guidelines, women in both arms will be offered an HIVST to bring home to their partners. In both arms, women will be instructed in the use and interpretation of HIVST and be provided up to two HIVST kits to give to or use with their male partners, per Ugandan Ministry of Health guidelines. After HIV testing and enrollment into the Kingasa study, HIV-negative male partners will be offered PrEP and HIV-positive men will be linked to ART. We will recommend that HIV-negative men take PrEP until their partner has been on ART for at least 6 months or longer if they report additional partners of unknown status.
- Aim 1:** To evaluate whether the proportion of male partners of pregnant HIV-positive women who test for HIV, is improved after distribution of a letter of invitation to a wellness visit (dual syphilis and HIV rapid test, blood pressure, visual acuity screening and COVID-19 screening) to their female partners compared to the standard of care (standard of care invitation letter from the clinic).
- Aim 2:** To evaluate whether POC viral load testing with same day ART adherence support improves viral suppression among pregnant and post-partum women living with HIV compared to standard of care lab-based HIV VL testing.

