Overall, 97% of HIV-negative partners in the Partners Demonstration Project initiated PrEP and had high adherence with tenofovir detected in 82% of plasma samples. Similarly, we observed high uptake and adherence to ART among HIV-positive partners; 91% initiated ART by 24 months with >90% viral suppression (47). The integrated PrEP and ART strategy accelerates ART initiation; 90% of HIV-positive partners initiated ART within six months, compared to 50% in the Partners PrEP Study (49). This integrated PrEP and ART strategy nearly eliminated HIV transmission with 95% reduction in HIV transmission (Figure 2) (47). High protection was observed among HIV-negative men (95% HIV reduction,  $p < 0.0001$ ), relevant to this project (50). We found PrEP until the HIV-positive partner initiated ART was highly acceptable, safe and effective (51). Thus, the Partners Demonstration Project provided strong evidence of high adherence and effectiveness of time-limited PrEP among HIV serodiscordant couples who were counseled about their risk of HIV exposure, who were young, and many wanted children, and were counseled about the efficacy of PrEP and ART. These findings provided critical data for PrEP guidelines by WHO (52, 53), Kenya (54), and Ugandan guidelines.

The primary difference with the Obumu is that the HIV serodiscordant couples had already mutually disclosed in the Partners Demonstration Project. In Obumu and our proposed Obumu 2 project, we are evaluating interventions to address the challenges of lack of disclosure by HIV positive pregnant women which is one of the barriers in reaching male partners to test for HIV. We thus are evaluating innovative strategies to reach the male partners of HIV positive pregnant women so that the men can learn their HIV status and benefit from PrEP if HIV negative, as in the Partners Demonstration Project described above, or link

to ART if HIV positive.

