## **STUDY METHODS**

### *Overall design*

This is a randomized factorial trial to assess two strategies; one to increase HIV testing and engagement  
Kingasa Study Protocol

in care among male partners of pregnant women, and the second to improving ART continuation and adherence among the HIV-positive pregnant women. The overall goal is to evaluate the impact of innovative strategies to increase male partner HIV testing, and engagement in HIV care and prevention among men and their pregnant partners, through ANC services provided to HIV- positive women.

We will recruit HIV-positive women with a partner of unknown HIV status through PMTCT B+ programs at Kitebi Health Center III in Kampala. Women will be randomized 1:1:1:1 to

- Arm 1: Women will be provided the standard of care invitation letter for male partners for fast-track visit for HIV testing and laboratory HIV testing at enrollment and every 6 months until 6 months postpartum,
- Arm 2: Women will be provided the standard of care invitation letter for male partners for fast-track visit for HIV testing and POC VL tests for women at enrollment, delivery, and 6 months post-partum;
- Arm 3: Women will be provided an invitation letter for male partners for wellness visits and laboratory-based HIV VL testing for women at enrollment, delivery, and 6 months post-partum;
- Arm 4: Women will be provided an invitation letter for male partners invitation letter for male partners for wellness visits and POC viral load testing for women at enrollment, delivery, and 6 months post-partum.

Women who are randomized to receive POC VL will receive same day ART adherence counseling and those randomized to receive lab based VL will receive VL results at their next visit with ART adherence counseling based on their VL results.

Male partners of women who are randomized to the wellness visit will receive a phone call from a male counselor after HIV testing to encourage linkage to care and prevention, depending on HIV status.

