### Follow up study procedures

All data collection will be conducted in a private room in the participant's preferred language, according to the participant's fluency and preference. Women in the intervention and control groups will be asked about their experience providing the intervention arm letter or control arm letter, as well as their partner's testing and outcome at their PMTCT visits. Women in the intervention and control groups whose partners do not come for testing, will be asked whether they discussed HIV testing with their partner, whether their partner was tested elsewhere, the outcome of his test, and whether any social harms resulted.

At each follow up visit, questionnaires will be administered to assess sexual behavior, self-perceived risk, partner testing status, intimate partner violence, relationship power, future fertility desires, self-efficacy, stigma, facilitators and barriers to ART and PrEP, social support, and symptoms of common mental disorders (Table 3).

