### Care for HIV-positive male partners

This study will identify male partners who are HIV-positive, either as part of testing male partners of unknown status, or during follow-up of initially HIV-negative men. Study staff will provide participants with their HIV test results in the context of post-test counseling. Men identified as HIV-positive will be referred for HIV clinical care, including primary care and antiretroviral therapy, according to Ugandan guidelines. During the course of the study, it is possible that guidelines will change regarding clinical care of persons with HIV (including optimal therapy, prophylaxis, etc.). At all times during the study, treatment and referral practices for HIV-positive persons in the study will adhere to national ART guidelines. After the study ends, HIV-positive participants will be provided referrals to other care programs for ongoing HIV primary care. This type of care will also be offered to initially HIV-negative study participants who become positive during follow-up.

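### The partner eligibility criterion joins two negated conditions with *or*, so read literally it admits men whose HIV status is known, against the stated unknown-status population

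*Protocol*

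**What the plan says.** The Eligibility section holds the only partner-status criterion that a screener can apply: "Male partner not known to be HIV-positive or has not tested in the past 3 months".

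Four other places in the protocol describe the couples to be recruited:

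- Summary, narrative: "women with partners of unknown status in order to evaluate whether an invitation to a wellness screening".
- Summary, Approach: "who have a male partner of unknown HIV status".
- Overall design: "We will recruit HIV-positive women with a partner of unknown HIV status".
- Population, immediately before Eligibility: "with male partners of unknown status".

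None of these says what unknown status means, and no other section does. The section on care for HIV-positive male partners lists the ways in which the study will identify positive men: "either as part of testing male partners of unknown status, or during follow-up of initially HIV-negative men". It sets no entry rule, but a man already known to be positive at entry fits neither route.

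**The concern.** Two exclusions have been written as negated inclusions and linked with *or*. A couple then qualifies if either limb is met. A man known to be positive qualifies as long as he has not been tested lately. A man known to have tested negative last month qualifies because he is not known to be positive. For both, the woman already knows the status.

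The criterion decides which couples are randomized in a trial whose first aim is to get untested men to test at the clinic. Three things are at stake: whether the enrolled population matches the stated one, whether staff screen consistently, and whether some enrolled men have less reason to respond to either letter, which would dilute the Aim 1 effect.

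**Working it through.** **Logic check.** Classify the partner by what the woman knows of his status (positive, negative, unknown) and by whether he was tested within three months. Three rules are compared:

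- Literal rule: not known positive *or* not recently tested.
- Plain *and*: not known positive *and* not recently tested.
- Knowledge-based *and*: not known positive *and* no known negative test within three months.

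| Partner | Literal *or* | Plain *and* | Knowledge-based *and* |
|---|---|---|---|
| Known positive, recent test | out | out | out |
| Known positive, no recent test | **in** | out | out |
| Known negative, recent test | **in** | out | out |
| Known negative, older test only | in | in | in |
| Result unknown, recent test | in | **out** | in |
| Result unknown, no recent test | in | in | in |
| Admitted | 5 of 6 | 2 of 6 | 3 of 6 |

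The two bold cells under the literal rule contradict the stated population. The bold cell under the plain *and* shows that swapping one word is not enough: it would turn away a man whose result the woman does not know. The man with only an older negative result counts as unknown status only if the protocol says so; the three-month limb suggests that this is meant.

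The one other way to parse the sentence lets *not* govern the whole phrase. That would require a recent test and exclude untested men, so it does not rescue the text.

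**Size, as illustration only.** The inputs from the protocol's power section and its table are 200 women, hence 100 per group in the factorial comparison, with control rates of 20%, 25% and 30% and detectable increases of 22, 21 and 20 points at 80% power. The protocol bases power on a log-rank test. I use a pooled two-proportion test at two-sided alpha 0.05 as an approximation:

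power = Φ{ [Δ√n − 1.96√(2p̄(1−p̄))] / √(p₁(1−p₁) + p₂(1−p₂)) }

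Undiluted, 30% vs 50%: (2.000 − 1.96 × 0.6928) / 0.6782 = 0.947, power 0.828. The other rows give 0.879 and 0.926, so all three meet the stated 80%.

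Now assume that a share f = 5% of partners (10 of 200) test at the control rate whichever letter they receive. The intervention rate becomes p₁ + (p₂ − p₁)(1 − f).

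| Planning row | Diluted intervention rate | Power before | Power after |
|---|---|---|---|
| 30% vs 50% | 0.30 + 0.20 × 0.95 = 49.0% | 0.828 | 0.789 |
| 25% vs 46% | 0.25 + 0.21 × 0.95 = 44.95% | 0.879 | 0.846 |
| 20% vs 42% | 0.20 + 0.22 × 0.95 = 40.9% | 0.926 | 0.901 |

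For 30% vs 50%: (1.900 − 1.96 × 0.6913) / 0.6782 = 0.804, power 0.789.

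A harsher assumption is that such men test in neither group, so both rates are multiplied by 1 − f. The 30% vs 50% row then gives 0.795 at f = 5%, 0.759 at 10% and 0.682 at 20%. If there are almost no such men, or they respond like the others, nothing is lost. The documents give neither f nor how these men would respond.

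**The case against.** The strongest reply is that the protocol resolves the point itself. The Population section stands directly above Eligibility and says whose partners are to be recruited, and the Summary and Overall design agree. The Background states the purpose as reaching men "so that the men can learn their HIV status and benefit from PrEP if HIV negative". On that reading, nobody would enrol a known-positive partner, and the *or* is a slip of drafting. This largely stands for the known-positive man. It does not settle the case of the man known to have tested negative recently: the first limb lets him in, the population statement keeps him out, and two careful screeners could decide differently.

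A second reply is that the enrolment interview described under Quantitative surveys asks what the woman knows of her partner's status, so such couples can be identified and described. That is true, and it limits the damage, but it does not correct the entry rule.

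A reader might infer three stronger things, none of which the documents support:

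- *That ineligible couples were enrolled.* The protocol reports no enrolment data.
- *That the Aim 1 comparison is biased.* Such couples fall in every arm by chance, and the intent-to-treat comparison remains valid.
- *That every recently tested partner is outside the population.* A man whose recent result the woman does not know is of unknown status, and the existing wording is right to admit him.

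**Conclusion.** The point holds in a limited form. The literal criterion contradicts the population stated in four places, because it admits two kinds of partner whose status is known. The cause is probably a drafting slip, but it sits in the only operational partner-status rule, with no definition of unknown status to fall back on.

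The consequences are a possible mismatch between the enrolled and stated populations, inconsistent screening, and some dilution of the Aim 1 effect. The size of the dilution cannot be estimated from the documents. The drop from 0.828 to 0.789 rests on an assumed 5% share, no response to the wellness letter among those men, and an approximation to the planned log-rank test. It shows sensitivity and is no evidence that the trial is underpowered.

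**What to change.** Reconcile the Eligibility criterion with the Summary, Overall design and Population sections by requiring both conditions, stated in terms of what the woman knows. For example: *Male partner is not known to be HIV-positive and is not known to have had a negative HIV test in the past 3 months.* The woman is the person screened, and the protocol already relies on her report elsewhere; at follow-up, women whose partners have not come are asked "whether their partner was tested elsewhere, the outcome of his test".

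Define unknown status once by this rule. State that a man with only an older negative result, or one tested recently whose result the woman does not know, stays eligible.

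If the team did intend either condition to suffice, leave the criterion and change the four population statements instead. Keep any couples already randomized in the intent-to-treat analysis.

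The cost is a one-line amendment and one definition. The eligible pool becomes slightly smaller, out of the roughly 50 HIV-positive women identified per month according to the Recruitment section.

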### *Sample size*

A total of 200 pregnant women living with HIV and their male partners.

### *Recruitment*

IDI Kasangati has long-established recruitment and retention strategies to identify and enroll participants for prospective follow up. Recruitment materials will be approved by the IRB before study initiation. Recruitment materials will educate women about the benefits of male partner testing, the probability of being HIV serodiscordant, safety and efficacy of PrEP, and risks of post-partum ART discontinuation for the woman's health and the possibility of HIV transmission to her baby and partner.

Women attending antenatal care are offered HIV testing, and those who test positive are provided immediate ART according to Uganda national HIV treatment and prevention guidelines. Approximately, 50 HIV-positive women are identified per month. IDI Kasangati will work directly with the Kitebi KCCA facility, including antenatal care/PMTCT programs, to identify pregnant HIV-positive women attending PMTCT B+ services. Health care workers and study staff at Kitebi ANC clinic will provide general information sessions to inform potential participants.

### *Study Enrollment*

Women will be enrolled and followed at the Kitebi ANC clinic. Trained research staff will counsel potentially eligible women about the benefits of male partner testing, post-partum ART persistence for HIV-positive women, PrEP safety and effectiveness for HIV-negative persons, and possible participation in the study. Counseling messages will include:

#### Reasons for male partners to be tested for HIV:

- To know his status.
- If he is positive that he does not infect others.
- If he is positive, to help him to access care and treatment which will help him stay

healthy longer.

- If he is negative, to help him stay HIV negative.
- To strengthen their relationship.
- To avoid testing by proxy since about half the time, he will have a different status than his partner.

HIV status disclosure:

- Does your partner know your status?
- If no, and you are positive, what do you think might happen if you discuss this with your partner?
- Where would you tell him? When would you tell him?
- Encourage women to tell him a story about the antenatal clinic, how other women have encouraged their partners to test for HIV, which has been beneficial for the family by keeping both partners health longer and see what kind of reaction he has.
- Importance of talking about HIV together with their partner so they can plan for the future.
- Risk of HIV for their children.
- Explore the possibilities of being sent away, relationship ending, violence, etc.

Intimate partner violence: The counselor will collect the following information in a culturally appropriate way:

- In the past month, has your current partner punched, slapped, kicked, bit you, or caused you any type of physical harm?
- In the past month, has your current partner insulted, ignored or humiliated you, yelled at you, or made you feel ashamed or bad about yourself?
- In the past month, has your current partner forced you to have sex or perform any sexual act, or touched you sexually in any way that you did not want?
- In the past month, has your current partner made you feel afraid, unsafe or in danger?
- In the past month, has your current partner taken your money when you didn't want him to, or prevented you from working outside the home?

Women who indicate a willingness to participate and have screened negative for recent or potential social harms will be asked to provide informed consent for study enrollment. Women will be asked if they would like a male study staff member to contact their partner directly by phone to encourage him to come to the clinic, per standard of care guidelines. Partners who come to clinic for a wellness visit or come for HIV testing in response to an invitation letter will be offered the opportunity to consent for study enrollment. Men will consent to participate in the study and receive open label PrEP or ART, depending on HIV status. Participants will be asked questions about their medical history, including specific questions about prior pregnancies, any medical problems, partner's status, HIV testing, and whether they think violence would result from offering an invitation letter with infographics about the components of a wellness visit or an invitation letter for fast-track HIV testing to provide their partner.

[figure not shown]
Each participant will be asked to provide independent informed consent for study participation. Women who meet eligibility criteria and are willing to participate in the study for 6 months post-partum, will be consented and enrolled. Trained clinicians will perform physical exams, including measurement of blood pressure, height, and weight.

Study procedures

Specific study procedures are depicted in Figure 3 and detailed in Table 1.

